#### 4.1.2 Treatment Period

Each subject visits the Investigative site at the beginning of the study for Visit 1 (Week 1) and the matched wounds are randomized (if entry criteria are met) and the assessment/treatment period begins and will continue for 25 weeks. Additionally, the subject will return to the Investigative site for a single day Safety Follow-up Visit 30 days ( $\pm 4$  days) from the last dose of B-VEC.

#### 4.1.2.1 Guidance for Subjects Enrolled under Previous Protocol Versions

Subjects enrolled under previous protocol versions, in which more than one (1) Primary Wound Pair was selected, will continue to receive their randomized treatment for the duration of the study. However, the Investigator will select a single matched pair, which most closely match in both size and anatomical location. This single Primary Wound Pair will be used for evaluation and will be included in the outcome measurements.

For subjects who had more than four (4) Secondary Wounds, no new Secondary Wounds will be selected, and treatment will continue on the previously selected Secondary Wounds for the study duration. If subjects had less than four (4) Secondary Wounds selected, the Investigator may select additional Secondary Wounds, until four (4) have been selected, not exceeding the Weekly Maximum Dose.

## 4.2 Study Visits

Study visit procedures are performed only after a signed informed consent / assent (as applicable) is obtained. During the study, every effort should be made to adhere to the visit schedule provided in the Schedule of Events ([Table 1](#)).

### 4.2.1 Sequence of Study Procedures

The following must be taken into account regarding the sequence of study procedures:

- Questionnaires should be completed with wound dressing removal during the visit. The EQ-5D and Skindex-29 may be administered at the end of the study visit, for the subject to complete, and return at their next scheduled visit.
- At scheduled visits (refer to [Table 1](#)) in which a urine pregnancy test must be completed, the test must result negative, prior to applying B-VEC or placebo, for women of childbearing potential, as determined by the Investigator.
- At visits in which blood is drawn, attempt collection of vital signs prior to the blood draw.
- On days in which B-VEC and placebo administration(s) occur, all study procedures and assessments must occur pre-dose.

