
Primary Endpoint
	
Wound Healing
 
The primary endpoint is the proportion of DEB primary wound sites with complete wound healing of the originally selected baseline wound in B-VEC versus placebo treated intra-subject wound sites at Weeks 22 and 24 or Weeks 24 and 26, as determined by the Investigator, to evaluate durability and repeat dosing. The complete wound healing is defined as 100% wound closure of the exact original wound surface area selected at baseline, specified as skin re-epithelialization without drainage.

Secondary Endpoints
	
Key Secondary Endpoint
 
 
• Proportion of the selected primary wound sites with complete wound healing of the exact wound surface area selected at baseline (as defined in the primary endpoint) in B-VEC-treated versus placebo at Weeks 8 and 10 or Weeks 10 and 12 (as determined by the Investigator) to evaluate durability.
 
 
Secondary Endpoint
 
 
• The mean change in pain severity using a VAS score per primary wound site associated with wound dressing changes at Weeks 22, 24 and 26 for each treated versus placebo wound, for ages 6 and above on the primary wound pair. For ages below 6 years, the Face Legs Activity Cry and Consolability-Revised (FLACC-R) scale will be used.
 

Exploratory Endpoints
	
 
• Relative time to wound closure from baseline.
 
• Duration of closure, as defined by the time from complete wound closure to the reopening of the Primary Wounds.
 
• The mean change in Quality of Life in addition to Skindex score as compared to baseline at Week 26.
 

Safety Endpoint
	
 
• The safety and tolerability of B-VEC based on the assessment of adverse events, physical examinations, vital signs, and clinical laboratory test results.
 

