
Study Treatment, Duration and Assessments
	
Study Treatment
 
Week 1
 
 
- Following randomization of the matched primary wound pair, wounds will receive one Weekly Treatment in a double-blinded manner.
 
- The Remaining Weekly Dose will be calculated and applied to a maximum of four (4) additional wounds (“Secondary Wounds”). Secondary Wound(s) will receive a Weekly Treatment of B-VEC. The number of Secondary Wound(s) treated will depend on wound area of the Secondary Wound(s). The total dose applied to Secondary Wound(s) is not to exceed the Remaining Weekly Dose.
 
 
Week 2 through 26
 
 
- Subjects will return to the clinical site for assessment of all wounds by the Investigator.
 
- The Primary Wound Pair will receive one Weekly Treatment in a double-blinded manner. However, if one of the wounds in a matched Primary Wound Pair closes completely and there are no open neighboring wounds, as determined by the Investigator during a weekly visit, then that particular wound and its neighboring wound/s will not receive Weekly Treatment that week. Once that particular wound, or its neighboring wound/s, is determined to be open by the Investigator at a weekly visit, Weekly Treatment will continue. If the originally selected primary wound closes, its neighboring wound/s may continue to receive treatment.
 
- If a Secondary Wound is closed completely, as well as its neighboring wound/s, as determined by an Investigator, during a weekly visit, then that particular wound and its neighboring wound/s will not receive Weekly Treatment that week. If the originally selected secondary wound closes, its neighboring wound/s may continue to receive treatment. The total dose applied to secondary wounds is not to exceed the Remaining Weekly Dose.
 
- Subjects will come to clinic for assessment even if the originally selected wounds are closed.
 
 
Safety Follow-up/Early Termination
 
 
- Subjects will return to the clinical site 30 days following the last dose of B-VEC.
 
- Subjects may roll into an Open Label Extension (OLE) Protocol. If subjects do not participate in the OLE Protocol, they will be asked to roll over into a Long-Term Follow-up Protocol (All subjects enrolled in the study who received at least a Weekly Treatment).
 
 
Assessments
 
 
- Safety measures include adverse events, physical examinations, vital signs, and clinical laboratory tests. All safety analyses results will be performed using the safety population. A summary of safety results will be presented for each treatment group.
 

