## Schedule of Events

**Table 1. Visit Assessments and Procedures**

Study Day	Randomized-Double Blinded Placebo-Controlled Treatment Period								Safety Follow-up/ET
	Screening 	Week 1	Week 2 -21	Week 22	Week 23	Week 24	Week 25	Week 26	30 days after last dose
Daily Visit Window	-60 to 0	na	± 3 days						± 4 days
Visit	Screening	1	2-21	22	23	24	25	26	SFU
Obtain Consent / Assent	X	X 							
Inclusion/Exclusion Criteria		X							
Demographics	X	X 							
Medical History	X	X 							
Genetic Testing	X 								
Wound Selection		X							
Wound randomization 		X							
Pain Assessment- Wound Pair 		X		X		X		X	
Quality of Life Questionnaire (EQ-5D) 		X						X	
Skindex Questionnaire 		X						X	
Imaging 		X	X	X	X	X	X	X	X
Assessment of Wound Closure 		X	X	X	X	X	X	X	
Swabs for Viral Shedding/Infectivity 		X	X	X	X	X	X	X	
Swabs for Viral Shedding on Dressing Returned 			X						

 If genetic testing is required, this test may occur up to 60 days prior to the other screening procedures, following subject consent/assent. Genetic testing may take 6-8 weeks to obtain results.

 Informed consent/assent, demographics, medical/ procedural history, urine (if male) and blood specimens will not be re-collected, if collected at a Screening visit.

 The matched primary wound pair will be randomized.

 Pain questionnaires are to be completed during the dressing change of the individual matched wounds. If subject is 6 years of age or older, they will be asked to complete the VAS questionnaire for matched wounds during the dressing change. If younger than 6 years of age, their parent/caregiver will be administered the FLACC-R questionnaire for the matched wounds during the dressing change (Refer to section 6.2.2).

 Both the Quality of Life (EQ-5D) and Skindex Questionnaires will be administered to subjects 12 years of age and older at the time of consent. Questionnaires may be administered for the subject to complete after the visit and bring back at the next scheduled visit.

 Images will be collected on both closed and open wounds. Image in the same order and orientation at each visit prior to IP application.

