15 Labs will be attempted, unless per the discretion of the Investigator, it is not in the best interest of the subject. If labs are attempted and not obtained, documentation will be noted in the study visit. Furthermore, if labs are not attempted, justification must be recorded in the study visit. The Investigator must determine clinical significance for out-of-range values.

16 Conduct all other study visit procedures prior to B-VEC and placebo administration. Matched Wounds: IP will be applied to wounds that are open. If a matched wound and neighboring wound is closed, no IP will be applied and application will be reinitiated once the wound reopens at a scheduled visit, as determined by the Investigator. Secondary Wounds: IP will only be applied to open wounds as determined by the Investigator, not to exceed the Remaining Weekly Dose. IP may be applied to immediate neighboring wounds. Up to four (4) unmatched Secondary Wounds may be selected to receive open-label B-VEC during the study treatment. Trace the area that is receiving treatment (including the neighboring wounds). Neighboring wounds are defined as wounds approximately 2-3cm away from the original matched and unmatched (Primary and Secondary) wound.

17 At the Safety Follow-up (30 days ± 4 days) following the last dose of B-VEC, subjects may roll over into an OLE protocol or will be asked to roll over into a LTFU protocol

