5.2 Baseline Definition

In general, baseline is defined as the value closest to but prior to administration with either B-VEC or placebo (Screening or Visit 1/ Week 1).

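### The take-home option for EQ-5D and Skindex-29 lets the Week 1 form be completed after the first dose, against the plan's own pre-dose rules, and leaves the timing of the Week 26 form loose

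*Protocol*

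**What the plan says.** **The endpoint.** The Protocol Synopsis lists as exploratory: "The mean change in Quality of Life in addition to Skindex score as compared to baseline at Week 26". SAP 7.5 (Additional Analysis) plans only a descriptive summary of the change in EQ-5D-5L and Skindex-29 from before treatment to after its end. Protocol 8.9 rules out imputation for exploratory endpoints.

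**The schedule.** Table 1 of the Schedule of Events places both instruments at Week 1 and Week 26 only, for subjects aged 12 and over at consent. Protocol 4.2.4 and 4.2.10 agree. Protocol 4.2.3 (Screening) lists neither.

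**The permission.** Protocol 4.2.1 makes completion during the visit the default for questionnaires, then exempts these two: they "may be administered at the end of the study visit, for the subject to complete, and return at their next scheduled visit". Footnote 5 is plainer: "Questionnaires may be administered for the subject to complete after the visit and bring back at the next scheduled visit". Neither text limits the option to a particular visit. SAP Appendix 1 carries the same footnote.

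**The opposing rules.** The last bullet of the same section 4.2.1 reads: "On days in which B-VEC and placebo administration(s) occur, all study procedures and assessments must occur pre-dose". Footnote 16 reads: "Conduct all other study visit procedures prior to B-VEC and placebo administration". SAP 5.2 states that, in general, "baseline is defined as the value closest to but prior to administration with either B-VEC or placebo". Protocol 8.7.1 and SAP 7 likewise take efficacy baselines from pre-dose measurements at Screening or Visit 1.

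**The concern.** A site that follows footnote 5 at Week 1 obeys one instruction and breaks another. It also produces a score that does not meet the plan's definition of baseline.

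No other value can stand in. There is one score before treatment and one at its end, and no Screening collection. The scores describe the whole subject, who receives B-VEC on one primary wound, placebo on the other, and open-label B-VEC on Secondary Wounds where these are selected. There is no concurrent control, so change from the subject's own baseline is the only estimate. If the baseline is given during the first treated week, that change may be shifted by an amount and in a direction that the documents give no means of judging.

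At the other end, the next scheduled visit after Week 26 is the Safety Follow-up. A form returned there may describe a time after treatment has stopped, although the endpoint is named for Week 26.

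**Working it through.** The plan states no figure on this point, so there is none to reproduce. The check is one of sequence, followed by simple day counts.

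**Step 1: is a take-home Week 1 form post-dose?**
- Week 1 is a dosing visit. The Synopsis says for Week 1: "Following randomization of the matched primary wound pair, wounds will receive one Weekly Treatment in a double-blinded manner". Table 2 marks product administration at Week 1.
- Footnote 16 puts all other visit procedures before product application, so application comes last.
- The end of the Week 1 visit, and any time after it, therefore falls after the first application.
- Set against this, 4.2.1 requires that "all study procedures and assessments must occur pre-dose" on such days. The permission and the rule cannot both be followed for a form completed after the Week 1 visit.

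**Step 2: does such a form count as baseline?** Under SAP 5.2, SAP 7 and Protocol 8.7.1, baseline is a pre-dose value. The form is post-dose and there is no Screening form. Read strictly, that subject has no baseline, and with no imputation (Protocol 8.9) no change score. Neither the protocol nor SAP 7.5 says what to do.

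**Step 3: how late can a Week 1 form be?**
- Inputs: weekly visits; Week 2 window of ±3 days (Table 1).
- Days from first dose to the Week 2 visit = 7 ± 3.
- Result: 7 − 3 = 4 to 7 + 3 = 10 days, nominally 7.

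**Step 4: how late can a Week 26 form be?**
- Input: Safety Follow-up at 30 ± 4 days after the last dose (Table 1; Protocol 4.2.12).
- Days from last dose to return = 30 ± 4, that is 26 to 34.
- The follow-up is tied to the last dose, not to Week 26. With the last dose at nominal week w, days from the Week 26 visit to return = (30 ± 4) − 7 × (26 − w):

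| Last dose (nominal week) | Days from Week 26 visit to return |
|---|---|
| 26 | 26 to 34 |
| 25 | 19 to 27 |
| 24 | 12 to 20 |

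**Step 5: what do these counts mean?** They are return times, so they only bound completion from above. A form may be filled in on the evening of the visit and handed back later. They also assume that the next visit takes place within its window.

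**Step 6: what else is touched?** The pain scales are not. Footnote 4 ties them to the dressing change itself, and the take-home wording covers only EQ-5D and Skindex. Wound closure assessments are not affected.

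**The case against.** The strongest reply is that little hangs on this. The endpoint is exploratory, has no test or alpha attached, and gets one descriptive line in the SAP. Take-home is an optional exception: completion during the visit is the default, and Protocol 4.2.4 lists both questionnaires well ahead of product administration. Nothing shows how often the option is used. All of that stands, and it limits the size of the point. It does not remove the contradiction, because the exception names exactly these two instruments and Week 1 is one of only two visits at which they are given.

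The Week 26 half is weaker, and this objection also stands. SAP 7.5 speaks of change from before treatment to after its end, and a form completed after the Week 26 visit fits that description. What remains is a mismatch with the Week 26 time point named in the protocol endpoint, and no stated window.

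It is also fair to say that SAP 5.2 opens with a general qualifier, so exclusion of a post-dose form is a strict reading and not a written rule. The case report form is not among the documents, so it may already capture a completion date.

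No evidence is offered that a first-week score differs materially from a pre-dose one. Protocol 1.2.1 reports COL7 expression as early as 48 hours after administration, so an effect within the 4 to 10 days cannot be excluded, but that says nothing about how the scores would move.

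Finally, on-site completion would not supply a control group. It would make the within-subject change mean what its name says, and no more.

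**Conclusion.** The point holds as an internal contradiction with a limited consequence. At Week 1 it is firm: the permission can yield a baseline given after the first dose, returned 4 to 10 days later, which the plan's own definitions do not accept and which nothing can replace. At Week 26 it is a looser matter: the form may be returned 26 to 34 days after the last dose and may not reflect the nominal time point.

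This rests on three readings: that the permission applies at both visits, since neither text restricts it; that product is applied last at the visit, as footnote 16 requires; and that the next visit is kept within its window.

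A reader might infer that the endpoint has neither a real baseline nor a real Week 26 value. The documents do not support that. The option may be used rarely, and the day counts are latest return times, not completion times. Nor do they support saying that most subjects had also been treated on Secondary Wounds by then: up to four may be selected, and no proportion is given. The effect is confined to the EQ-5D and Skindex-29 summaries in subjects aged 12 and over. The primary, key secondary and pain endpoints are unaffected.

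**What to change.** 1. In Protocol 4.2.1, Schedule of Events footnote 5 and the same footnote in SAP Appendix 1, remove the take-home option at Week 1. Require both instruments to be completed on site before the first product application.
2. At Week 26, require completion on site. Alternatively, record the completion date and set a short window in days in SAP 7.5 for a form to count as Week 26.
3. For subjects already enrolled, whose Week 1 visit cannot be repeated, state in SAP 7.5 that a Week 1 form known to have been completed after the first dose is not used as baseline. Report how many subjects this affects.

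The cost is slightly longer Week 1 and Week 26 visits and, if the case report form lacks one, a completion-date field. Some enrolled subjects may lose a change score under item 3. Without the take-home option a few forms might be missed altogether. Keeping a dated take-home form at Week 26 limits that risk; at Week 1 a late form would not serve as a baseline in any case.

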### 4.2.2 Protocol Deviations

Any deviations from the protocol are discouraged. A protocol deviation will be defined as any excursion from the protocol, or any instance of protocol noncompliance. If deviations do occur, the Principal Investigator must inform the monitor/Sponsor, and the implications of the deviation must be reviewed and discussed. Any paper documentation must be kept in the Investigator's File or Subject Binder and the Sponsor will file in the TMF. If the Investigator determines a deviation is necessary, they are to contact the Sponsor prior to the occurrence for approval, if time permits.

### 4.2.3 Screening

If a subject has not undergone genetic testing, which is needed for inclusion criteria, they may visit the site up to 60 days prior to Visit 1 (Week 1). The genetic test may take 6 to 8 weeks to obtain results.

- Review and signature of informed consent form/assent
- Collection of demographic data (e.g. sex, age, race, and ethnicity)
- Obtain Medical History
- Treatment/Procedural review

- Obtain Medication History
- Obtain Genetic testing specimens
- Collection of urine for viral shedding
- Collection of blood for clinical laboratory tests:
  - o Complete Metabolic Panel with Direct Bilirubin
  - o Complete Blood Count with Differential and Platelets
  - o HSV and COL7 Serum ADA
  - o Whole blood for viral shedding

#### **4.2.4 Week 1/Visit 1 (First Day of Treatment Cycle)**

- Review and signature of informed consent form/assent, if not previously obtained at Screening.
- Collection of demographic data (e.g. sex, age, race, and ethnicity), if not previously obtained at Screening
- Obtain Medical History, if not previously obtained at Screening
- Treatment/Procedural review
- Medication review
- Inclusion/Exclusion
- Selection of two (2) matched wounds to be assessed as Primary Wounds and selection of up to four (4) Secondary Wounds (not to exceed the Remaining Weekly Dose)
- Primary Wound Pain Questionnaire
  - FLACC-R (Subjects less than 6 years of age)
  - VAS (Subjects 6 years of age and older)
- Quality of Life Questionnaire (Subjects 12 years of age and older)
- Skindex Questionnaire (Subjects 12 years of age and older)
- Selection of Secondary Wounds depending on the Remaining Weekly Dose
- Wound imaging of all selected wounds
- Assess selected wounds
- Physical exam
- Vital signs
- Collection of skin swabs for viral shedding and infectivity from all the selected primary wounds
- Collection of urine for a pregnancy test, if applicable as determined by the Investigator
- Collection of urine for viral shedding, if not collected at Screening
- Collection of blood for clinical laboratory tests, if not collected at Screening:
  - Complete Metabolic Panel with Direct Bilirubin

- Complete Blood Count with Differential and Platelets
- HSV and COL7 Serum ADA
- Whole blood for viral shedding
- Randomization of wound pair
- IP administration
- AE/SAE review

**4.2.5 Week 2 through 21**

- Medication review
- AE/SAE review
- Treatment/Procedural review
- Wound imaging of all selected wounds
- Assess Primary Wound Closure at Visit 8, 10, and 12 only
- Assess Secondary Wound/s
- Vital signs will be collected at Visit 5, 9, 13, 17, 21, and 25 only
- Collection of skin swabs for viral shedding and infectivity from all the selected Primary Wounds
- Collection of bandage swabs for viral shedding from all the Primary Wounds, if applicable
- IP administration

**4.2.6 Week 22**

- Medication review
- AE/SAE review
- Treatment/Procedural review
- Primary Wound Pain Questionnaire
  - FLACC-R (Subjects less than 6 years of age)
  - VAS (Subjects 6 years of age and older)
- Wound imaging of all selected wounds
- Assess Primary Wound Closure
- Assess Secondary Wound/s
- Collection of skin swabs for viral shedding and infectivity from all the selected Primary Wounds
- Collection of bandage swabs for viral shedding from all the Primary Wounds, if applicable
- IP administration

**4.2.7 Week 23**

- Medication review

- AE/SAE review
- Treatment/Procedural review
- Wound imaging of all selected wounds
- Assess Secondary Wound/s
- Collection of skin swabs for viral shedding and infectivity from all the selected Primary Wounds
- Collection of bandage swabs for viral shedding from all the Primary Wounds, if applicable
- IP administration

**4.2.8 Week 24**

- Medication review
- AE/SAE review
- Treatment/Procedural review
- Primary Wound Pain Questionnaire
  - FLACC-R (Subjects less than 6 years of age)
  - VAS (Subjects 6 years of age and older)
- Wound imaging of all selected wounds
- Assess Primary Wound Closure
- Assess Secondary Wound/s
- Collection of skin swabs for viral shedding and infectivity from all the selected Primary Wounds
- Collection of bandage swabs for viral shedding from all the Primary Wounds, if applicable
- IP administration

